6.3.1.2. TEAEs by System Organ Class and Preferred Term

Summary tables of TEAEs by SOC and PT up to 28 days, and throughout the study after the IP administration by using frequency counts and percentages of participants with an event will be provided for:

- All unsolicited TEAEs*
- All serious TEAEs*
- All unsolicited treatment-emergent AESIs*
- All unsolicited severe TEAEs*
- All unsolicited TEAEs that are medically-attended*
- All unsolicited TEAEs leading to discontinuation from participation in the study

* Tables will also be presented for treatment-related TEAEs up to 28 days after IP administration.

6.3.2. Solicited Adverse Reactions

The SARs are recorded by the participant in eDiary on the day of injection and for the 6 days post injection. If a solicited local or systemic AR starts more than 7 days after dosing, it should be captured on the AE page until resolution, not to exceed 28 days after vaccination. If a solicited local or systemic AR continues beyond 7 days post injection, the participant should notify the site to provide an end date and close out the event. ARs beyond Day 7 should be reviewed by the clinic staff either during the next scheduled telephone call or at the next clinic visit, or during an unscheduled visit.

Analyses of SARs within 7 Days will be provided based on the Solicited Safety Set. Analyses of SARs with Onset after Day 7 will be provided based on the Safety Set. The following summaries will be provided

- Summary of SAR Within 7 Days (SAR eDiary and SAR eCRF)
 - i. The number and percentage of participants who reported individual solicited local AR and/or solicited systemic AR during the 7-day follow-up period after the injection will be tabulated by severity grade, and by severity grade and day of reporting.

A two-sided 95% exact confidence interval (CI) using the Clopper-Pearson method will be provided for the percentage of participants who reported any solicited local AR, solicited systemic AR, or any SAR.

- ii. The number and percentage of participants who reported individual solicited local AR and/or solicited systemic AR during the 7-day follow-up period after the injection will be summarized by onset day (Day 1 through Day 7). The onset of individual SAR is defined as the time point after the injection at which the respective SAR first occurred.
- Summary of SAR with Grade 3 or higher
 - i. The number and percentage of participants who reported individual Grade 3 and/or higher solicited local AR and solicited systemic AR during the 7-day follow-up period after the injection will be tabulated by severity grade, and by severity grade and day of reporting.
- Summary of SAR Duration (SAR eDiary and SAR eCRF)
 - i. The duration of SAR in days will be calculated as the last date the SAR is reported - the first date the SAR is reported + 1.
- Summary of SAR Persisting Beyond 7 Days (SAR eDiary and SAR eCRF)
 - i. The number and percentage of participants who reported individual solicited local AR and/or solicited systemic AR that persist beyond 7 days after the injection (i.e., occurred before day 7, but persisting after day 7 regardless of duration) will be tabulated by severity grade.

A two-sided 95% exact confidence interval (CI) using the Clopper-Pearson method will be provided for the percentage of participants who reported any solicited local AR, solicited systemic AR, or any SAR persisting beyond 7 days after injection.

- Summary of SAR with Onset after Day 7 (AE eCRF)
 - i. The incidence of solicited local ARs and solicited systemic ARs with onset day after the 7-day follow-up period after the injection (i.e., after Day 7) will be tabulated.
 - ii. The onset day of solicited local ARs and solicited systemic ARs with onset day after the 7-day follow-up period after the injection (i.e., after Day 7) will be summarized descriptively.

- iii. The duration of SAR in days for solicited local ARs and solicited systemic ARs with onset after the 7-day follow-up period after the injection (i.e., after Day 7) will be summarized descriptively, similar to SAR duration summary.
- Summary of Onset Day for Local Reactions (SAR eDiary and SAR eCRF)
 - i. The number and percentage of participants who reported local reactions will be tabulated by onset day (within 7 days and beyond). The onset day is defined similarly in ‘Summary of SAR Within 7 Days’ section.

6.3.3. Pregnancy Tests

A point-of-care urine pregnancy test will be performed for all female participants of childbearing potential at the Screening Visit and before the vaccine dose on Day 1, if Day 1 is not on the same day as the Screening Visit. At any time, a pregnancy test either via blood or point-of-care urine can be performed, at the discretion of the investigator. The participant’s follicle-stimulating hormone (FSH) level may be measured at the Screening Visit, as necessary, and at the discretion of the investigator, to confirm postmenopausal status.

A by-subject listing will be provided for pregnancy tests with positive results.

6.3.4. Vital Sign Measurements

Vital sign measurements, including systolic and diastolic blood pressures, heart rate, respiratory rate, and body temperature, will be collected at the time points indicated in the SoE tables in the protocol with pre- and post-dosing on the day of injection (Day 1) only and they will be presented in a listing. The abnormalities meeting the toxicity grading criteria (Grade 2 or higher) in any vital sign measurement will be provided in the listing.

If a participant has a vital sign result with Grade 2 or higher abnormality at any post injection visit, then all results of vital sign measurement for that participant will be presented in the listing.

Shift from baseline in the toxicity grades at each time point and shift from baseline in the toxicity grades to the worst post-baseline result will also be summarized.

6.4. Immunogenicity Analysis

The analyses of immunogenicity will be based on the PPSI-Neg analysis population and will be performed by treatment group as defined in [Section 6.1](#).

The GMT and GM levels will be calculated using the following formula:

$$10^{\left\{ \frac{\sum_{i=1}^n \log_{10}(t_i)}{n} \right\}}$$

where t_1, t_2, \dots, t_n are n observed immunogenicity titers or levels.

The GMFR measures the changes in immunogenicity titers within participants. The GMFR will be calculated using the following formula:

$$10^{\left\{ \frac{\sum_{i=1}^n \log_{10}\left(\frac{v_{ij}}{v_{ik}}\right)}{n} \right\}} = 10^{\left\{ \frac{\sum_{i=1}^n \log_{10}(v_{ij}) - \log_{10}(v_{ik})}{n} \right\}}$$

where, for n participants, v_{ij} and v_{ik} are observed immunogenicity titers or levels for participant i at time points j and k , $j \neq k$.

6.4.1. Immunogenicity Assessments

Blood samples for immunogenicity assessments will be collected at the time points indicated in the SoE ([Appendix E](#)). The following immunogenicity assessments will be measured:

- Serum bAb level against SARS-CoV-2 as measured by ligand-binding assay specific to the SARS-CoV-2 S protein and the S protein RBD (MSD multiplex assay).
- Serum neutralizing antibody (nAb) level against SARS-CoV-2 as measured by pseudovirus neutralization assays.

[Table 5](#) outlines the bioassays that will be implemented to assess the immunogenicity endpoints.

With the purpose of measuring the neutralizing antibody titers against the BA.4/BA.5 variants, VAC137 assay will be analyzed as part of the exploratory analysis and will only be assessed at Day 1 and Day 29 in a randomly-selected subgroup of participants from each study part, 4th dose group only. A total of 200 participants from each study part (n=400 participants total) comprising 160 baseline SARS-CoV-2 seronegative and 40 baseline SARS-CoV-2 seropositive participants were sampled from the PPSI population. The study was stratified at randomization by age group and the distribution of participants ≥ 65 years was 35% in Part 1 and 33.5% in Part 2. The random sample from each study part fixed the distribution of participants ≥ 65 years at 35%, when feasible.

Table 5 Immunogenicity Assays

Strain/Antigen	Method	Assay Name
Prototype	Pseudovirus neutralization	VAC62
Omicron BA.1 (BA.1.1.529)	Pseudovirus neutralization	VAC122
Omicron BA.4/BA.5	Pseudovirus neutralization	VAC137
S, RBD, Omicron (B.1.1.529), Delta (AY.4), Gamma (P.1), Alpha (B.1.1.7), Beta (B.1.351)	Multiplex binding antibody ECL	MSD VAC123-8 plex

6.4.2. Analysis of the Immunogenicity Endpoints

6.4.2.1. Part 1 (mRNA-1273.529 and mRNA-1273)

6.4.2.1.1. Primary and Key Secondary Analyses

For the primary objective on immune response for the second booster (4th dose) of mRNA-1273.529, there are two primary hypotheses to be tested (see [Section 4.2](#)). The primary analysis set for immunogenicity objectives will be based on PPSI-Neg.

Day 29 (alpha=0.01, two-sided)

For the first primary hypothesis, an analysis of covariance (ANCOVA) model will be performed to assess the difference in immune response between mRNA-1273.529 and mRNA-1273 against the B.1.1.529 strain at Day 29 in the subgroup of participants who received the 4th dose. Antibody titers at Day 29 post-booster against the B.1.1.529 strain will be a dependent variable, and a group variable (mRNA-1273.529 and mRNA-1273) will be the fixed effect, adjusting for age groups (≥ 16 to < 65 , ≥ 65 years), most recent COVID-19 vaccination type (mRNA or viral vector) and pre-booster antibody titer level, if applicable. The GMT will be estimated by the geometric least square mean (GLSM) from the model and corresponding 99% CI will be provided for each group. The GMR (ratio of GMTs) for mRNA-1273.529 with respect to mRNA-1273 will be estimated by the ratio of GLSM from the model with 99% CI. The 99% CI for GMR will be used to assess the between group difference in immune response against the B.1.1.529 strain for mRNA-1273.529 at Day 29 compared to the mRNA-1273 as a booster for non-inferiority testing.

Month 3 (alpha=0.04, two-sided)

The same ANCOVA model described above will be used to assess immune response of mRNA-1273.529 against the B.1.1.529 strain at Month 3. The 96% CI for GMR will be used to assess the between group difference in immune response against the B.1.1.529 strain for non-inferiority.

The primary immunogenicity objective (against the B.1.1.529 strain) is considered met if the non-inferiority is demonstrated based on a GMR at either Day 29 or Month 3. Specifically, against the B.1.1.529 strain, the non-inferiority of immune response of mRNA-1273.529 as compared to mRNA-1273 will be considered demonstrated if the lower bound of the corresponding 99% CI of the GMR is ≥ 0.67 (Day 29) based on a non-inferiority margin of 1.5 or the corresponding 96% CI of the GMR is ≥ 0.67 (Month 3) based on a non-inferiority margin of 1.5.

Once non-inferiority against B.1.1.529 is demonstrated, superiority of mRNA-1273.529 as compared to mRNA-1273 against B.1.1.529 will be tested (key secondary hypothesis). Specifically, superiority of mRNA-1273.529 as compared to mRNA-1273 will be demonstrated if the lower bound of the 99% CI of the GMR is > 1 (Day 29) or the lower bound of the 96% CI of the GMR is > 1 (Month 3).

Supportive analyses of the primary and key secondary immunogenicity endpoints at Day 29 and Month 3 will also be performed in the PPSI. These analyses will be based on the ANCOVA model described above and will include the pre-booster/baseline SARS-COV-2 status (negative, positive, or missing) as a factor. The 99% CI for GMR will be used to assess differences between groups at Day 29 and the 96% CI for GMR at Month 3.

6.4.2.1.2. Secondary Analyses

The ANCOVA model described in [Section 6.4.2.1.1](#) will be used for secondary analyses to assess for immune response of mRNA-1273.529 compared to mRNA-1273 booster administered as a 3rd or 4th dose at all measured time points. Antibody titers against the B.1.1.529 strain will be a dependent variable, and a group variable (mRNA-1273.529 and mRNA-1273) will be the fixed effect, adjusting for age groups (≥ 16 to < 65 , ≥ 65 years), most recent COVID-19 vaccination type (mRNA or viral vector) and pre-booster antibody titer level, if applicable. The GMT will be estimated by the GLSM from the model and its corresponding 95% CIs will be provided for each group. The GMR for mRNA-1273.529 with respect to mRNA-1273 will be estimated by the ratio of GLSM from the model and the corresponding 95% CIs will be provided. No hypothesis tests will be performed for these objectives.

For each antibody of interest, the GMT or level with corresponding 95% CI at each time point, and GMFR of post-baseline titers or levels over baseline with their corresponding 95% CIs at each post-baseline time point will be provided. The 95% CIs will be calculated based on the t-distribution of the log-transformed values then back-transformed to the original scale for presentation. The following descriptive statistics will also be provided at each time point: number of participants (n), median, minimum, and maximum. Additionally, reverse cumulative distribution plots and box plots of titers or levels will be generated for each antibody of interest and for any subgroups of interest (e.g., age group).

The mixed effects model repeated measure (MMRM) will be used to analyze all post-booster measures including treatment group, analysis visit, treatment by visit interaction, age groups and pre-booster titer levels (if available) as fixed effects and participant as a random effect. An unstructured covariance structure will be used to model the within-participant errors. The compound symmetry structure will be used when the model fails to converge. The GMT will be estimated from the model and its corresponding 95% CI will be provided for each group at each post-boost timepoint. The GMR for mRNA-1273.529 with respect to mRNA-1273

will be estimated from the model and the corresponding 95% CI will be provided at each post-boost timepoint.

PPSI will be used as the analysis population to summarize the immune responses (antibodies of interest) and the above summary statistics including GMT and GMFR will be provided by pre-booster/study baseline SARS-CoV-2 status.

The SRR is measured by an increase of SARS-CoV-2-specific bAb or nAb titer or value (level) from pre-booster below the lower limit of quantification (< LLOQ) to at least 4 x LLOQ, or a 4-fold or greater rise if pre-booster \geq LLOQ.

The SRR will be summarized at all measured time points for each treatment group with the 95% CI calculated using the Clopper-Pearson method. The difference of SRRs at all measured time points for mRNA-1273.529 compared with mRNA-1273 will be provided with 95% CI using Miettinen-Nurminen method. Analysis of the SRR will be performed in the PPSI-Neg. A sensitivity analysis of SRR will be performed in the PPSI by using stratified Miettinen-Nurminen method, with pre-booster positive, negative, and unknown SARS-CoV-2 status as strata.

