4.2. Scientific Rationale for Study Design

This 2-phase study includes a randomized, blinded phase (Phase A) and an open-label, observational phase (Phase B). Phase A is designed as a 2-part, randomized, stratified, observer-blind, active-controlled study to demonstrate the immunogenicity and safety of the mRNA-1273.529 and mRNA-1273.214 vaccine in medically stable individuals 16 years and older. Participants will receive a single dose of either mRNA-1273.529/mRNA-1273.214 or mRNA-1273 (active comparator) booster vaccine as the 3rd or 4th dose of a COVID-19 vaccine.

Because it is possible that participants are exposed to SARS-CoV-2 through community exposure, NP swab samples and the serologic assays will be collected before vaccination on Day 1 to help discriminate between natural infection and vaccine-induced antibody responses, should such discrimination be needed. Furthermore, NP swab specimen(s) for assessment of pathogens including SARS-CoV-2, will also be collected at any time during the study period if participants have symptoms suggestive of COVID-19 or other upper or lower respiratory infection at the investigator's discretion. Additionally, clinical information will be collected to evaluate the severity of the clinical case.

Following authorization of the mRNA-1273.214 booster, the study was amended to allow a transition to Phase B, the open-label, observational phase. Transitioning the study to the open-label, observational phase allows eligible participants in either treatment arm in Part 1 and Part 2 to receive an additional booster outside of the study after completing the Month 6 and Month 3 study visit, respectively.

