Immunogenicity, SARS-CoV-2-specific bAb and nAb, will be assessed at multiple time points in this study. Mixed effects models will be used to analyze all post-booster/baseline measures. The models will include treatment group, analysis visit, treatment by visit interaction, and adjustment for age groups and pre-booster titer levels. An unstructured covariance structure will be used to

model the within-participant errors. The GMT will be estimated from the model and its corresponding 95% CI will be provided for each group at each post-boost timepoint. The GMR (ratio of GMTs) for mRNA-1273.529 and for mRNA-1273.214 with respect to mRNA-1273 will be estimated from each model and the corresponding 95% CI will be provided at each post-boost time point.

For each of the antibodies of interest (eg, levels of SARS-CoV-2-specific bAb and SARS-CoV-2-specific nAb), the GMT or level with corresponding 95% CI at each time point, and GMFR of post-booster/pre-booster titers or levels with corresponding 95% CI at each post baseline time point will be provided for each arm. The 95% CIs will be calculated based on the t-distribution of the log-transformed values then back-transformed to the original scale for presentation. The following descriptive statistics will also be provided at each time point: number of participants (n), median, minimum, and maximum. PPSI will be used as the analysis population to summarize the immune responses (antibodies of interest) and will the above summary statistics including GMT and GMFR will be provided by pre-booster/study baseline SARS-CoV-2 status.

SRR definitions and analyses will be defined in the SAP.

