4.1. Overall Study Design

The study is a Phase 2/3, two-part, randomized, observer-blind, active-controlled, multicenter study to evaluate the immunogenicity and safety of mRNA-1273.529 and mRNA-1273.214 booster vaccine in medically stable individuals 16 years and older. The

mRNA-1273.529 vaccine contains mRNAs encoding for the S-2P of the SARS-CoV-2 Omicron variant (B.1.1.529). The mRNA-1273.214 vaccine contains mRNAs encoding for both the S-2P of the SARS-CoV-2 Wuhan Hu-1 strain and the S-2P of the SARS-CoV-2 Omicron variant (B.1.1.529), formulated in the same LNP.

The study consists of 2 parts with 2 phases each:

In **Part 1**, approximately 600-1000 participants will be randomized in a 1:1 ratio to 1 of 2 study arms to receive a single dose of either 50 µg of mRNA-1273.529 or 50 µg of mRNA-1273 (active control). Randomization will be stratified by age groups (16 to < 65 years or ≥ 65 years) and number of booster doses received (to receive study vaccine as the 4th dose or to receive study vaccine as the 3rd dose). At least 90% of participants will receive the study vaccine as the 4th dose.

In **Part 2**, approximately 2,924 participants will be randomized in a 1:1 ratio to 1 of 2 study arms to receive a single dose of either 50 µg of mRNA-1273.214 or 50 µg of mRNA-1273 (active control). Randomization will be stratified by age groups (16 to < 65 years or ≥ 65 years) and number of booster doses received (to receive study vaccine as the 4th dose or to receive study vaccine as the 3rd dose). At least 90% of participants will receive study vaccine as the 4th dose.

Each part has a Phase A (randomized, blinded) and Phase B (open-label, observational). Phase B was designed to offer eligible participants in either treatment arms in Part 1 the option to obtain an additional booster after their Month 6 assessment and eligible participants in either treatment arm in Part 2 the option to obtain an additional booster after their Month 3 assessment. The additional booster will be obtained outside of the study.

The potential number of participants in each arm and the randomization ratio can be found in [Table 2](#). The study schema is shown in [Figure 1](#).

Table 2 Study Arm and Dose Levels

Part 1

Vaccination Group	Vaccination Received	Total Dose	N (total)	Study vaccine as the 3 rd dose	Study vaccine as the 4 th dose
1	mRNA-1273.529	50 µg	300- 500 ^a	30-50	270-450
2	mRNA-1273 (Active Control)	50 µg	300- 500 ^a	30-50	270-450

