6.4.2.2.2. Secondary Analyses

The same ANCOVA model described above will be used for secondary analyses to assess for immune response of mRNA-1273.214 compared to mRNA-1273 booster administered as a 4th dose against other variants at Day 29 or Month 3. The GMT will be estimated by the GLSM from the model and its corresponding 95% CIs will be provided for each group. The GMR for mRNA-1273.214 with respect to mRNA-1273 will be estimated by the ratio of GLSM from the model and the corresponding 95% CIs will be provided. No hypothesis tests will be performed for these objectives.

SRR of the mRNA-1273.214 booster administered as a 4th dose against the B.1.1.529 strain, prototype strain and other variants of concern (VOC) will be analyzed in the PPSI-Neg using the methods as described in [Section 6.4.2.1.2](#). A sensitivity analysis of SRR will be performed in the PPSI by using stratified Miettinen-Nurminen method, with pre-booster positive, negative, and unknown SARS-CoV-2 status as strata.

MMRM as described in [Section 6.4.2.1.2](#). will be used to assess immune response mRNA-1273.214 against both the B.1.1.529, the prototype strain, and other VOC at all measured timepoints after study vaccine administration.

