6.6. Planned Analyses

The planned interim analyses of immunogenicity and safety will be performed after participants have completed Day 29 and Month 3 in both Part 1 and Part 2. Analyses of the Month 6 and Month 12 visit including Phase B (open-label, observational) will be exploratory. The final analysis of all endpoints will be performed after all participants have completed or discontinued from the study. Results of the final analysis will be presented in a final clinical study report (CSR).

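### The SAP's MMRM carries a redundant participant random effect with compound symmetry as its only fallback; two cheap additions would separate late titres and adverse events after an outside COVID-19 booster (minor)

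*SAP*

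**What the plan says.** **Model.** SAP 6.4.2.1.2 opens with "The mixed effects model repeated measure (MMRM) will be used to analyze all post-booster measures including treatment group". It enters visit, treatment by visit, age group and pre-booster titre "as fixed effects and participant as a random effect. An unstructured covariance structure will be used to model the within-participant errors". On failure, "The compound symmetry structure will be used when the model fails to converge". SAP 6.4.2.2.2 reuses the model in Part 2 for B.1.1.529, "the prototype strain, and other VOC at all measured timepoints after study vaccine administration". Protocol 9.6.1 has the same fixed terms and unstructured errors: "The models will include treatment group, analysis visit, treatment by visit interaction, and adjustment for age groups and pre-booster titer levels". It names no participant random effect and no fallback. SAP Section 7 reports no change from the protocol.

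**Outside boosters.** Protocol 4.2 explains: "Following authorization of the mRNA-1273.214 booster, the study was amended to allow a transition to Phase B". SAP 4.1 opens this after Month 6 in Part 1 and gives "eligible participants in either treatment arm in Part 2 the option to obtain an additional booster after their Month 3 assessment".

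**Safety.** SAP 6.1 ends the whole-study safety period at completion, discontinuation or death. SAP 6.3.1.2 tabulates adverse events over that period, and SAP 5.8 assigns them to the study vaccine received. SAP 3.1.2 makes SAEs, medically attended AEs (MAAEs) and AESIs from Day 1 to end of study part of the primary safety endpoints.

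**Status.** SAP 6.6: "Analyses of the Month 6 and Month 12 visit including Phase B (open-label, observational) will be exploratory".

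**The concern.** There are three separable issues.

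1. **Specification error.** An unstructured covariance already contains everything a random intercept can describe. Fitting both leaves one parameter undetermined. Some programs set the surplus variance to zero; others may fail to converge and so trigger the fallback. Compound symmetry imposes one variance on all visits. Visit-level intervals are then too narrow where titres are more variable and too wide elsewhere.
2. **Late titres.** The overall MMRM pools titres from participants who have and have not taken an outside booster by Month 12 (Part 1) or by Month 6 and Month 12 (Part 2). No visit-level rule is stated for it. Mixing the two groups is also one reason late variance could be larger.
3. **Late adverse events.** The whole-study tables do not show which events followed another COVID-19 vaccine.

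**Working it through.** The plan gives no figure on these points to reproduce. Uptake and titre rise are not given, and the log-titre SD is redacted, so those values below are assumptions shown as ranges.

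**1. Identifiability.** Post-boost humoral visits are Days 29, 85, 179 and 359 (SAP 4.1, Appendix E), so T = 4.
- Unstructured: T(T+1)/2 = 10 parameters, rank 10.
- Adding a random intercept gives V = s²J + R, with J a matrix of ones. Replacing (s², R) by (s² + c, R − cJ) leaves V unchanged. That is 11 parameters, rank 10.
- Numerical check: in one simulated four-visit data set the log-likelihood was −475.788474 at random-intercept variances 0, 0.1, 0.2, 0.3 and 0.4.
- Compound symmetry has 2 parameters, rank 2. If the random intercept is kept there, it has 3 parameters, still rank 2.

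**2. Follow-up open to an outside booster.**
- Visit schedule: Part 1 (358 − 178)/358 = 180/358 = 50%; Part 2 (358 − 84)/358 = 274/358 = 77%. These are ceilings.
- Calendar: Amendment 2 is dated 26 August 2022 (SAP Section 1), and the estimated last completion is 07 April 2023 (protocol synopsis). That is 224 days, and 224/358 = 63% in Part 2.

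**3. Cost of compound symmetry.** Assume fraction p boosted, a fold rise f, variance SD² at unmixed visits, and SD² + p(1−p)(ln f)² at mixed visits. True error of a nominal 5% is 2[1 − Φ(1.96 √(mean variance / visit variance))].
- Worked case: p = 0.5, f = 4, SD = 0.8, only Month 12 mixed (Part 1). Mixed variance = 0.64 + 0.25 × 1.922 = 1.120. Mean variance = (3 × 0.64 + 1.120)/4 = 0.760. √(0.760/1.120) = 0.824, and 1.96 × 0.824 = 1.61, giving 10.6%.

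| p = 0.5; SD 0.8 to 1.5 | Error at mixed visits | Error at Day 29 |
|---|---|---|
| f = 4, Month 12 mixed (Part 1) | 10.6% to 6.8% | 3.3% to 4.4% |
| f = 4, Months 6 and 12 mixed (Part 2) | 8.2% to 6.1% | 2.2% to 3.9% |
| f = 2, Month 12 mixed (Part 1) | 6.6% to 5.5% | 4.5% to 4.8% |

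**4. Overall late GMR.** If boosting brings boosted participants in both arms to the same titre (assumed), the overall GMR is G^(1−p). For G = 1.5 this is 1.5^0.7 = 1.33 at 30% uptake and 1.5^0.2 = 1.08 at 80%.

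**5. Setting titres aside by visit.** The interval widens by √(R² + (1−R²)/(1−p)), with R² = kρ²/(1 + (k−1)ρ) and k earlier visits retained. At assumed p = 0.6 and ρ from 0.85 to 0.5, Month 12 widens 1.14 to 1.39 times in Part 1 (k = 3) and 1.15 to 1.41 times in Part 2 (k = 2).
- Example, k = 2, ρ = 0.5: R² = 0.5/1.5 = 0.333, and √(0.333 + 0.667/0.4) = 1.41.

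**6. What the text settles.**

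| Place | What it does | What it leaves open |
|---|---|---|
| Protocol 6.5.3 | An outside COVID-19 vaccine can affect per-protocol evaluability | Discretionary |
| SAP 6.2.6 | Deviation rules fixed before database lock | Content not given |
| SAP 6.1, 6.4.2.1.3, 6.4.2.2.3 | Immunogenicity by Phase B booster subset | Splits whole participants after randomisation; no visit-level rule for the overall MMRM |
| SAP 6.1 | Safety by the same subgroups | Optional |
| SAP 6.2.4, 6.3.1.1, 6.5.4 | Listings: non-study vaccinations; deaths, SAEs and AESIs; unsolicited AEs in infected participants | Partial case-by-case tracing; no general MAAE listing |
| SAP 6.5.2 | Ends efficacy person-time at the outside booster | Efficacy only |

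**The case against.** **The covariance point is largely wording.** Harm needs a chain: the program fails, compound symmetry is used, and variances differ by visit. Ten parameters are few beside the planned 270-450 (Part 1) or 1328 (Part 2) fourth-dose participants per arm, before exclusions. This stands as a limit on size. It does not defend the random effect, which serves no purpose here.

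**Handling of boosted titres exists.** Immunogenicity by Phase B subset is planned, and in Part 1 the cross-reference to earlier methods can be read as including the MMRM. Deviation rules may add more. The overall estimate is readable as a treatment-policy comparison. All of this stands, so the second issue is an improvement rather than an error.

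**The safety tables deliver the stated endpoint.** They do, the listings allow some tracing, and 28 days is the primary safety period.

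**Stronger readings that the documents do not support.**
- A reader might infer that the redundancy biases GMRs or intervals. It does not; the marginal covariance is unchanged.
- A reader might infer that a primary result is at risk. The confirmatory analyses are ANCOVAs at Day 29 and Month 3, and outside boosting is scheduled after those visits.
- A reader might take 77% of Part 2 follow-up as actual post-booster exposure. It is a visit-schedule ceiling.
- A reader might take it as certain that the late GMR drifts toward 1. That holds only if outside boosting brings the arms closer together.

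**Conclusion.** The participant random effect is wrong as written and departs from the protocol model. The single-step fallback is weak. The late-visit MMRM and the adverse-event summary are worthwhile, low-cost additions; no passage commits to either.

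The effect is conditional. Interval miscalibration arises only if the fallback is used and variances differ, and the table above rests on assumed uptake, rise and SD. With a 2-fold rise it is near nominal. No hypothesis test, primary endpoint or 28-day safety summary changes, and the late immunogenicity analyses are exploratory. This is a minor, low-severity correction.

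**What to change.** 1. **Covariance.** In SAP 6.4.2.1.2 delete the participant random effect, which restores the protocol model. If the unstructured fit still fails, try a structure with visit-specific variances, such as heterogeneous Toeplitz, before compound symmetry. The cost is wording only.
2. **Late titres.** Keep the overall MMRM. Add one late-visit version that sets aside titres taken after an outside COVID-19 vaccine and keeps that participant's earlier visits. Label it a hypothetical estimand under missing-at-random. The cost is one extra model and wider late intervals (step 5). Boosting is self-selected and may follow unblinding, so missing-at-random cannot be tested. No further ANCOVA is needed beyond the planned Phase B subsets.
3. **Adverse events.** Keep the Day 1 to end-of-study tables. Add one summary stopped at the first non-study COVID-19 vaccine, with later events shown separately. Protocol 6.5.2 already requires those vaccines to be recorded throughout the study, so no new data are needed.
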